Study Protocol and Statistical Analysis Plan

Evaluation of Extended Wear Technology

V 2.0

December 20, 2021

NCT04882800

Evaluation of Extended Wear Technology

1 Background

Since its original launch in 2008, the Lyric device has offered hearing impaired patients an invisible and more convenient option when compared to conventional daily wear hearing aids. Designed to be worn in the ear canal for several weeks or months at a time, this extended wear, non-custom hearing aid has gone through several iterations and product improvements in the last decade. These product improvements included an expanded size offering in 2017. However, even with this expanded size offering, discomfort, migration, feedback and sound quality still account for a large number of trial cancellations. These issues are often caused by a less than ideal fit, especially if a patient has narrowing ear canal.

2 Objectives

The primary objective is to determine if patients who have rejected or cancelled Lyric subscriptions within the last two years due to discomfort or feedback, migration or poor sound quality (due to poor fit) rate the investigational Lyric4 devices with a fitting modification as more comfortable than the conventional Lyric4 devices.

There are no secondary objectives.

3 Description of the investigational device

The Lyric4 device is an analog hearing instrument that is deeply inserted in the ear canal. It consists of an electronic module and two seals, a medial and lateral, glued onto the electronic module. Currently, the Lyric4 is available in seven non-custom sizes: XXS, XS, S, M, L, XL, and XXL. The investigational device is made of the same components of the commercially available Lyric4 device, but with a fitting modification which may allow for an improved fit for narrower ear canals and increase the size options.

4 Design of the clinical investigation

This will be an interventional, single group design with two conditions (Lyric4 and Lyric4 with fitting modification) where subjects will wear the currently available Lyric device in one ear and the investigational device in the opposite ear for two weeks; and then switch ears for two additional weeks. Subjects will be blinded as to which device is in each ear.

5 Risks and benefits of the investigational device and clinical Investigation

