The product-related risks and the clinical investigation procedure-related risks are well-controlled during the clinical investigation as the subject is under the care of a well-established, Lyric-trained, hearing health care provider. Any ear health risk from this investigation is no greater than any risk a hearing impaired patient experiences when undergoing a Lyric trial with a certified Lyric provider.

The study may reveal that the investigational devices are more comfortable for those patients who were unable to wear Lyric devices previously, thus implying an improved fit rate. The investigational devices are not custom, and do not require extensive modifications of the Lyric component itself. If improved fit rate can be confirmed, it is

likely that more hearing impaired patients who would like to experience the benefits of an extended wear device would be able to do so.

6 Endpoints

To satisfy the primary objective, subjective questionnaires will be administered after each device fitting and removal. Question domains may include, but are not limited to, comfort, occlusion, feedback, sound quality, and purchasing interest.

7 Inclusion and Exclusion Criteria

Inclusion criteria: Hearing loss N2-N4 (mild to moderate)

Hearing impairment: Any (conductive or sensorineural)

Population: Adults

Minimum Age: 18 years

Maximum Age: 90 years

Other: Previous Lyric users who rejected or cancelled Lyric trials or subscriptions due to discomfort, feedback, migration, or poor sound quality due to fit issues.

Exclusion criteria: Participants who can only wear a size XXS Lyric will be excluded as even an XXS investigational device would likely not be any more beneficial than a conventional XXS Lyric4 device.

Asymmetrical hearing loss

Other diagnosis that may cause fluctuations in hearing (i.e. Meniere's disease)

Unable to tolerate the physical fit of a Lyric device

Inability to be seen for 4 lab visits

8 Measurements and procedures

Investigation related procedures:

Study Procedure	Impact on subject	Standard of care?
Audiogram; may be done if most recent audiogram is more than 12 months old	Assesses hearing loss	Yes
Cerumen management	Clears ear canal of wax	Yes
Ear mold impression; may be done for future analysis of ear shape	Takes custom impression of ear	Yes

Fit with Lyric devices	Provides prescriptive amplification	Yes

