In the event of an adverse event, the investigation manager will make contact with the principal investigator within 24 hours to align on reporting procedures and to evaluate the relationship of the investigational device and the related procedure.

In the event of a serious adverse event, this will be reported to the FDA using Reporting Form FDA 3500, or by telephone at [name].

Confirmed UADEs will be reported to the IRB within 10 days after receiving notice of the event. If it is determined that an event or effect presents an unreasonable risk to subjects, this study, or those parts of the study presenting that risk, will be terminated no later than 5 working days after the determination is made and no later than 15 working days after Sonova USA first received notice of the event.

A causal relationship towards the medical device or investigation procedure should be rated as follows:

Not related: The relationship to the device or procedures can be excluded.

Unlikely: The relationship with the use of the device seems not relevant and/or the event can be reasonably explained by another cause, but additional information may be obtained.

Possible: The relationship with the use of the investigational device is weak but cannot be ruled out completely. Alternative causes are also possible.

Probable: The relationship with the use of the investigational device seems relevant and/or the event cannot be reasonably explained by another cause.

Causal relationship: The serious event is associated with the investigational device or with procedures beyond reasonable doubt.

Device deficiencies that might have led to an SAE are always related to the medical device.

The causality assessment of the SAE will be conducted according to MDCG 2020-10/1 Safety Reporting in Clinical Investigations of Medical Devices under Regulation (EU) 2017/745.

The reporting of Serious Adverse Events and Device Deficiencies follows the Regulation (EU) 2017/745 and the MDCG 2020-10/1 Safety Reporting in Clinical Investigations of Medical Devices under Regulation (EU) 2017/745.

17 Vulnerable Populations

The investigation does not include any vulnerable populations.

18 Suspension or premature termination of the clinical investigation

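### Section 16's causality levels do not match their own lead-in: the affirmative levels name only the modified device, the middle levels omit procedures, and the top level is worded for serious events

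*Combined protocol and SAP*

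**What the plan says.** Section 16 opens the scale with a broad scope: "A causal relationship towards the medical device or investigation procedure should be rated as follows". The five levels that follow vary in what they cover.

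- The lowest level is as broad as the lead-in: "Not related: The relationship to the device or procedures can be excluded".
- The next keeps the device unqualified but does not mention procedures: "Unlikely: The relationship with the use of the device seems not relevant".
- *Possible* narrows to one device: "The relationship with the use of the investigational device is weak but cannot be ruled out completely".
- The next does the same: "Probable: The relationship with the use of the investigational device seems relevant and/or the event cannot be reasonably explained by another cause".
- *Causal relationship* brings procedures back but is tied to seriousness: "The serious event is associated with the investigational device or with procedures beyond reasonable doubt".

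Section 3 uses the term investigational device for the Lyric4 with the fitting modification, as distinct from the commercial Lyric4. Under Section 4, "subjects will wear the currently available Lyric device in one ear and the investigational device in the opposite ear for two weeks", after which the ears are switched for two more weeks. Section 16 collects device deficiencies and all adverse events, serious or not. It also has the investigation manager and principal investigator evaluate relationship for any adverse event, but that sentence again names only the investigational device and the related procedure. Section 9 promises a safety analysis after data collection and does not say how events will be tabulated.

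**The concern.** Every subject wears both devices at the same time, one in each ear. Subjects had rejected or cancelled Lyric for reasons that include discomfort and poor fit (Section 7), so ear complaints are foreseeable with either device. A rating scale for this design has to be able to say that an event is related to whichever device was in the affected ear, or to a procedure such as cerumen management or an ear impression (Section 8).

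If the affirmative levels are open to one device only, similar events in the two ears receive different ratings because of the wording. Raters who follow the level text and raters who follow the lead-in will also disagree. Any later summary restricted to related events would inherit both problems, and it would lean against the modified device, the only one that the affirmative levels name.

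**Working it through.** The plan gives no figure to reproduce, and the point does not depend on sample size, alpha or power. The check sets the lead-in beside each level.

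| Text in Section 16 | Device named | Procedures named | Limited to serious events |
|---|---|---|---|
| Lead-in | unqualified | yes | no |
| Not related | unqualified | yes | no |
| Unlikely | unqualified | no | no |
| Possible | investigational only | no | no |
| Probable | investigational only | no | no |
| Causal relationship | investigational only | yes | yes |

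Of the five levels, 3 name only the investigational device, and these are all of the affirmative ones. Procedures appear in 2 of 5. One of 5 is limited to serious events.

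Four kinds of event, taken through the literal wording:

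1. *Event caused by the conventional Lyric4.* *Not related* and *Unlikely* are open; *Possible*, *Probable* and *Causal relationship* are not. *Unlikely* may even attract the event, since the comparator can be treated as another explanation.
2. *Clear-cut non-serious event caused by the modified device.* *Probable* is open, but the top level requires a serious event. The rating is capped at *Probable*.
3. *Non-serious event caused by a procedure.* *Possible* and *Probable* do not name procedures, and the top level requires a serious event. No affirmative level fits.
4. *Serious event caused by a procedure beyond doubt.* *Causal relationship* fits. If the link is less certain, the middle levels again do not name procedures.

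Exposure affected by case 1, from Section 4, for a subject who completes both two-week periods:

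- Days per ear: 2 × 14 = 28.
- Ear-days in total: 2 ears × 28 = 56.
- Ear-days on the conventional Lyric4: 14 in one ear + 14 in the other = 28.
- Share: 28 / 56 = 50%.

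This is a share of exposure. To turn it into a share of events, let r be the event rate per ear-day on the modified device divided by that on the conventional device. With equal ear-days, the share of device-caused ear events that arise on the conventional device is 1 / (1 + r). At r = 1, an assumption, it is 1 / 2 = 50%. It is above half if r is below 1 and below half if r is above 1. The documents give no event rate for either device.

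Other text that might close the gap: the cited European guidance is invoked for causality of serious adverse events, so on the protocol's own words it does not govern the non-serious events in cases 2 and 3, or a non-serious event in case 1. Section 9 states no tabulation by device that would offset the wording.

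**The case against.** The strongest reply is that the lead-in governs. It speaks of the medical device without qualification, as do the two lowest levels and the sentence on device deficiencies that might have led to a serious event. The second limb of *Probable*, about the absence of another reasonable cause, can also be stretched to the comparator. A sensible rater could read the whole scale as covering both devices. This stands in part: the defect is an inconsistency that raters may resolve differently, and the comparator is not expressly excluded. But the generic reading conflicts with Section 3's use of the term, and the evaluation sentence in Section 16 repeats the narrow wording.

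For serious events, the cited guidance may resolve some of this. Its content is not in the documents, so that stays open.

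Several stronger readings are tempting, and the documents do not support them:

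- *That procedures and non-serious events cannot be rated at all.* Procedures are in the lead-in and in the lowest and highest levels, and four of the five levels have no seriousness limit.
- *That the safety analysis will be one-sided.* All adverse events are collected whatever the device, and no tabulation by relatedness is planned. The risk applies to a summary of related events only.
- *That Section 9 must test the Section 5 statement, "Any ear health risk from this investigation is no greater than any risk a hearing impaired patient experiences".* That sentence justifies the risk of taking part. The only objective is comfort, and no safety comparison is planned.
- *That the weeks after the switch add another half of the ear-days to the problem.* Those 28 ear-days include 14 on the conventional device that are already counted, so the union is 28 + 28 − 14 = 42 of 56. Prior exposure to the other device comes from switching ears, and the rating scale does not create it.
- *That the adverse event form lacks the needed fields.* The form is not among the documents. Section 14 does require dates of use to be recorded.

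**Conclusion.** The point holds as a mismatch between the lead-in and the levels of the Section 16 scale, and it should be corrected. Applied literally, the scale has no affirmative level for events in the conventional-Lyric4 ear, which is 50% of ear-days in a subject who completes both periods. It caps clear-cut non-serious events from the modified device at *Probable* and gives non-serious procedure-caused events no affirmative level.

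The consequence is a risk of one-sided attribution against the modified device. It becomes real only if raters follow the level text over the lead-in and the results are summarised by relatedness. Saying that about half of device-caused ear events would go unattributed needs, in addition, equal event rates on the two devices, which the documents neither state nor contradict. The comfort objective is not affected.

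**What to change.** In Section 16:

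- Word every level for *the study device in the affected ear (Lyric4 or modified Lyric4) or a study procedure*.
- In *Causal relationship*, refer to any event instead of a serious one.
- Make the same change of scope in the sentence on how the investigation manager and principal investigator evaluate relationship after an adverse event.

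For each ear event, ensure that the record holds the ear, the device in it at onset, and the onset date. If the existing form already has these fields, nothing need be added.

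In Section 9, state that the safety analysis will be reported by the device worn in the affected ear. A descriptive count is enough, and it fits the exploratory status of the study.

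The cost is a few lines of text and, at most, three fields on a form. No visit, test or change in the care of subjects is involved.
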